### **9.7.2.3.2 Secondary Endpoint(s)**

*All adverse events:*

Subject incidence proportions (and 95% CIs) for all AEs collected in this study (see Sections 11.2.1 to 11.2.3) will be summarised and tabulated by system organ class and preferred term, and preferred term only. Incidence tables will also be presented with respect to time on Blincyto at the patient level (incidence rate) and event level (event rate). Tables will be presented overall, and by seriousness (serious, fatal) and severity (grade  $\geq$  3, grade  $\geq$  4, events leading to discontinuation of Blincyto, events leading to interruption of Blincyto) of event. Tables relating to AEs will also be summarised by the patient subgroups listed in Section 9.7.2.3.4. Tables will additionally be presented for AEs that are considered related to Blincyto treatment.

*Efficacy:*

Summaries of endpoints outlined in Section 9.3.2.2 in relation to efficacy overall and KM summaries as described in Section 9.7.2 will be performed. The assessment of MRD may also be performed by method of MRD assessment (PCR or flow cytometry). The 1-year and 100-day mortality after allogeneic HSCT will be summarised with the 1-year and 100-day KM rate and the additional KM summaries described in Section 9.7.2. For this endpoint, OS will be measured starting from the date of allogeneic HSCT in the subset of patients who undergo an allogeneic HSCT and OS endpoint summaries will be provided as described in Section 9.7.2.

*Blincyto utilisation & select health care resource use:*

Summaries of endpoints outlined in Section 9.3.2.2 in relation to Blincyto utilisation & select health care resource use will be summarised.

**9.7.2.3.3 Other Safety Analyses**

Subject incidence of serious adverse events (SAEs) that occur from 31 days after completion of Blincyto treatment until the start of another anti-cancer treatment, HSCT or for up to 1 year, whichever is earliest, will be tabulated overall and by system organ class and preferred term, and preferred term only. Subject incidence for SAEs will also be summarised by time interval (during Blincyto treatment and 3 month intervals after completion of treatment).

#### 9.7.2.3.4 Subgroup Analysis

Specified outcomes will be presented by the following subgroups of interest:

| Subgroup  | Safety Outcomes | Efficacy Outcomes |
|---|-----------------|-------------------|
| Patient subgroups other than Adult RR Ph- ALL (potentially including MRD+ ALL, ph+ ALL, paediatric ALL, NHL)                            | Yes             | Yes               |
| Country   | Yes             | Yes               |
| Age groups, in years at initiation of Blincyto (Paediatric: 0-11, Adolescent: 12-17, Adult: $\geq 18$ and $< 65$ , Elderly: $\geq 65$ ) | Yes             | Yes               |
| Patients with HIV positivity or chronic infection with hepatitis B virus or hepatitis C virus at initiation of Blincyto                 | Yes             | -                 |
| Patients weighing less than 45 kg   | Yes             | -                 |
| Patients with recent allogeneic HSCT prior to initiation of Blincyto  | Yes             | -                 |
| Patients with prior allogeneic HSCT at initiation of Blincyto   | -               | Yes               |
| Patients with recent or concomitant treatment with other anti-cancer therapies (including radiotherapy)                                 | Yes             | -                 |
| Patients with recent or concomitant treatment with other immunotherapy  | Yes             | -                 |

### 9.8 Quality Control

#### 9.8.1 Study Documentation and Archive

The Investigator is to maintain a list of appropriately qualified persons to whom he/she has delegated study duties. All persons authorized to make entries and/or corrections on eCRFs will be included on the Amgen Delegation of Authority Form.

Source documents are original documents, data, and records from which the patient eCRF data are obtained. These include but are not limited to hospital records, clinical and office charts, laboratory and pharmacy records, diaries, microfiches, radiographs, and correspondence.

The Investigator and study staff are responsible for maintaining a comprehensive and centralized filing system of all study-related (essential) documentation, suitable for inspection at any time by representatives from Amgen and/or applicable regulatory authorities.

Documents to be maintained for the study are as follows:

- Patient files containing the completed CRF, informed consent forms, as applicable, and patient identification list
- Study files containing the protocol with all amendments, copies of pre-study documentation, and all correspondence to and from the Institutional Review Board (IRB)/Independent Ethics Committee (IEC) or other relevant ethical review board and Amgen

In addition, all original source documents supporting entries in the eCRFs must be maintained and be readily available. Retention of study documents will be governed by the contractual agreement with Amgen.

Amgen retains all data, programs and outputs generated for the study. At study close, data are uploaded from the Medidata Rave database and stored in accordance with Amgen SOPs. Statistical programming and outputs are locked in the analysis environment and no updates are permitted; standard programming procedures will apply.

### **9.8.2 Study Monitoring and Data Collection**

Source data verification will be performed at the study site, in accordance with Amgen SOPs. The Amgen representative(s) and regulatory authority inspectors are responsible for contacting and visiting the Investigator for the purpose of inspecting the facilities and, upon request, inspecting the various records of the clinical study (eg, eCRFs and other pertinent data) provided that patient confidentiality is respected.

The clinical monitor or designee is responsible for verifying the eCRFs at regular intervals throughout the study to verify adherence to the protocol completeness, accuracy, and consistency of the data; and adherence to local regulations on the conduct of research. The clinical monitor, or designee is to have access to subject medical records and other study-related records needed to verify the entries on the eCRFs in accordance with the local laws and regulations.

The Investigator agrees to cooperate with the Clinical Monitor, or designee to ensure that any problems detected in the course of these monitoring visits, including delays in completing eCRFs, are resolved.

In accordance with the sponsor's audit plans, this study may be selected for audit by representatives from Amgen's Global Compliance Auditing function (or designees). Review of study-related records will occur to evaluate the study conduct and compliance with the protocol, and applicable regulatory requirements.

Data capture for this study is planned to be electronic:

- All source documentation supporting entries into the eCRFs must be maintained and readily available.
- Updates to eCRFs will be automatically documented through the software's "audit trail".
- To ensure the quality of clinical data across all patient and sites, a clinical data management review is performed on subject data received at Amgen. During this review, subject data is checked for consistency, omissions, and any apparent discrepancies. To resolve any questions arising from the clinical data management review process, data queries and/or site notifications are created in the EDC system database for site resolution and closed by Amgen reviewer.
- The Investigator signs only the Investigator Verification Form for this electronic data capture study. This signature indicates that the Investigator inspected or reviewed the data on the eCRF, the data queries, and site notifications, and agrees with the content.

### **9.8.3 Investigator Responsibilities for Data Collection**

The Investigator is responsible to comply with the protocol requirements for all assessments and data as stipulated in the protocol for each patient in the study.

### **9.8.4 Validity and Reliability**

The data collected for this study will derive from patient records that are kept for the documentation and decision-making regarding patient care. Abstractors will be trained on the eCRF, prior to the start of data collection for the study. Automatic edit checks within the database and further manual review by the sponsor help to ensure quality and completeness of the data. Data queries are sent to site for clarification and resolution of discrepancies.

### **9.9 Limitations of the Research Methods**

An important limitation will relate to missing information since the data for this study will be abstracted from medical charts. The eCRF will prompt recording of any information that is available, but the data being abstracted were recorded for patient care and not research purposes.

This study will not have an internal comparator group. Because Blincyto will be indicated for patients with Ph- B-precursor R/R ALL, the current treatment options for these patients are very limited; thereby, limiting an appropriate comparator group. Data from the clinical trials and historical control data prior to Blincyto introduction will be used to provide a context for this study.

This study will not limit the patient population to adults with the target indication (Ph- B-precursor R/R ALL). Medical charts for any patients receiving Blincyto will be eligible for abstraction; thus, patients who receive blinatumomab for other indications with market authorisation (eg, adult MRD+), or off-label, will be included in the study population. The safety and efficacy profile could differ among the different indications and could affect the overall profile of the study; however, events will also be stratified by the different Blincyto indications. The sample size for off-label use is expected to be small, but it is important to document any cases of off-label use. The safety and efficacy profile could also differ according to patient characteristics and disease status and the overall profile demonstrated by the study will be limited to the sample of patients included in the study.

In countries where patient informed consent is required to access medical records, selection/volunteer bias could be an issue if, for example, sicker patients are less likely to consent. In order to address bias against sicker patients who may have poorer prognoses, deceased patient data will be included in the study, subject to local laws, regulations, and any required consent approvals as applicable.

Information bias is another possible bias if, for example, the information for more complicated patients was recorded with more or less detail. Additionally, there may be missing information on AEs as underreporting of less SAEs in the medical record may occur. Finally, only medication errors that are recorded in the medical records will be captured which may result in an underestimation of medication errors. For instance, medication errors that did not reach patients, were not caught, or were not recorded because they did not result in any AE to the patient, may not be systematically recorded in medical records.

The sites to be included in this study are expected to be larger treatment centres that specialize in treatment of patients with ALL due to the size of the patient population even though an effort will be made to include smaller treatment centres for representative purposes. Therefore, there might be a bias towards larger centres where a difference in medical practice or patient mix compared with smaller treatment centres could exist and this could affect generalizability of the study findings.

Healthcare resource use is likely to depend on country-specific requirements on how Blincyto treatment is administered to patients. Therefore, the overall summary of healthcare resource use will be biased towards the countries included in the study.

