#### **9.2.3.2 Exclusion Criteria**

- Medical records of patients who have participated in Blincyto clinical trials will be excluded since their treatment will be prescribed by the study protocol unless the patient is receiving new Blincyto treatment outside the clinical trial.
- Medical records of patients participating in other Amgen non-interventional prospective studies in which safety endpoints are collected will be excluded
- Medical records of patients who have received Blincyto via an expanded access/compassionate use program will be excluded
- In countries where informed consent is required for access to medical records (in line with local laws and regulations): if such consent is not provided but is mandatory, the patient will be excluded.

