#### 9.3.1 Exposure Assessment

All patients included in this study will be or will have been exposed to Blincyto at their entry into the study. Exposure will be described in several ways:

- Duration of exposure (in days)
- Total cumulative dose ( $\mu\text{g}$ )
- Number of cycles completed (0-5)

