#### *Efficacy*

- Proportion of patients achieving CR (defined as < 5% bone marrow blasts, platelets > 100,000 cells per  $\mu\text{L}$ , and absolute neutrophil count > 1,000 cells per  $\mu\text{L}$ ) within 2 cycles of Blincyto treatment
- Proportion of patients achieving CR/CRh\*/Cri
- CR defined as < 5% bone marrow blasts, platelets > 100,000 cells per  $\mu\text{L}$ , and absolute neutrophil count > 1,000 cells per  $\mu\text{L}$ , or
  - CRh\* defined as  $\leq$  5% bone marrow blasts, platelets > 50,000 cells per  $\mu\text{L}$ , and absolute neutrophil count > 500 cells per  $\mu\text{L}$ , or
  - CRi defined as  $\leq$  5% bone marrow blasts and incomplete recovery of peripheral blood counts) within 2 cycles Blincyto treatment
- Proportion of patients receiving allogeneic HSCT. Defined for the subset of subjects who achieved CR.
- 1-year and 100-day mortality proportion after allogeneic HSCT. Defined for the subset of subjects who achieved CR.
- Relapse-free survival (RFS) time – defined as time from CR/CRh\*/CRi until relapse (proportion of blasts in bone marrow > 5% or blasts in peripheral blood after documented CR/CRh\*/CRi) or death. Defined for the subset of subjects who achieved CR.
- Disease free survival (DFS): defined as time from initiation of Blincyto (for minimal residual disease-positive [MRD+] patients at Blincyto initiation) until date of relapse or death
- Overall survival (OS) time – defined as time from initiation of Blincyto until death
- Proportion of patients with MRD among those who achieve CR/CRh\*/CRi within two cycles of Blincyto treatment - hematologic MRD detected by polymerase chain reaction (PCR) (or flow cytometry) at a level of  $1 \times 10^{-4}$  or higher.
- Efficacy outcomes (as described above) among patient subgroups defined by demographic and clinical factors (described in Section 9.7.2.3.4)

*Blinicyto utilisation & select health care resource use*

- Blincyto utilisation, for example:
  - Duration of Blincyto use (eg, number of completed cycles, total number of days of Blincyto administration)
  - Dosing pattern (eg, proportion of patients with step-up on day 8, number of cycles initiated, frequency of bag changes)
  - Proportion of patients with treatment changes (eg, interruption, discontinuation, dose reduction) as indicated by the SmPC after AEs (stratified by type of event)
- Select healthcare resource use, for example:

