### **9.7.2 Planned Method of Analysis**

All analyses will be descriptive. Continuous variables will be summarised by mean, median, standard deviation, 25th percentile, 75th percentile, minimum and maximum. Categorical variables will be summarised by number and percentage. For categorical outcomes, 95% confidence intervals will also be presented where appropriate. For time-to-event endpoints, Kaplan-Meier (KM) curves and estimates (median, 1st and 3rd quartile) of the time-to-event endpoint with 95% confidence intervals will be calculated, if estimable. Six, 12- and 24-month survival proportions and 95% confidence intervals will also be estimated. Tables will be presented for the total patient population (ie, those who meet the eligibility criteria and have at least one dose of Blincyto) split by adult and paediatric patients and for disease subgroups with 15 or more patients, as well as for the subset of patients with LFR. Safety and efficacy data will also be tabulated by the patient subgroups described in Section [9.7.2.3.4](#).

The Medical Dictionary for Regulatory Activities (MedDRA) version 24.1 or later will be used to code all adverse events.

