### 10.1 Informed Consent

For countries, where informed consent is required from patients, an initial sample informed consent form will be provided by Amgen for the Investigator to prepare the informed consent document to be used at his or her site. Updates to the template are to be communicated formally in writing from the Amgen Clinical Study Manager to the Investigator. The written informed consent document is to be prepared in the language of the potential subject population.

Where required by participating clinical sites for the collection of anonymized medical chart data, before a patient's participation in the study, the Investigator is responsible for obtaining written informed consent, where applicable by local regulations, from the subject or legally acceptable representative. The acquisition of informed consent is to be documented in the patient's medical records, and the informed consent form is to be signed and personally dated by the subject or legally acceptable representative and by the person who conducted the informed consent discussion. The original signed informed consent form is to be retained in accordance with institutional policy, and a

copy of the signed consent form is to be provided to the patient or legally acceptable representative. If a potential patient is illiterate or visually impaired and does not have a legally acceptable representative, the Investigator must provide an impartial witness to read the informed consent form to the patient and must allow for questions. Thereafter, both the patient and the witness must sign the informed consent form to attest that informed consent was freely given and understood.

Where required by local laws and regulations, consent will be sought from appropriate parties for the inclusion of deceased subject's data.

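### Where consent is mandatory and neither deceased patients' charts nor proxy consent can be used, patients must survive to consent, yet OS and DFS run from Blincyto initiation; 9.9 does not name this bias

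*Protocol*

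**What the plan says.** **Entry can follow treatment.** Section 9.3.1: "All patients included in this study will be or will have been exposed to Blincyto at their entry into the study". Section 9.2.4 has charts reviewed when a site joins and every 4 months after that. Section 9.2.3.1 makes eligible the record of anyone who started Blincyto in routine practice after national reimbursement.

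**Consent is a condition of entry where the law requires it.** Section 9.2.3.2: "if such consent is not provided but is mandatory, the patient will be excluded". Section 10.1 sets the timing: "before a patient's participation in the study, the Investigator is responsible for obtaining written informed consent, where applicable by local regulations". It does not tie consent to the date of initiation.

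**Deceased patients are included conditionally.** Section 9.9: "deceased patient data will be included in the study, subject to local laws, regulations, and any required consent approvals as applicable". Sections 9.2 and 10 allow next of kin or another body to consent, Section 10 mentions a consent waiver, and Sections 10.1 and 10.3 provide for consent for deceased patients' data. All of this follows local law.

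**Survival is counted from initiation.** Section 9.3.2.2: "Overall survival (OS) time – defined as time from initiation of Blincyto until death", and, for MRD-positive patients, "Disease free survival (DFS): defined as time from initiation of Blincyto". Section 9.7.2 prescribes Kaplan-Meier and adds: "Six, 12- and 24-month survival proportions and 95% confidence intervals will also be estimated". It does not say that a patient enters the risk set at consent or enrolment.

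**The limitation that is named.** Section 9.9 discusses volunteer bias, in that sicker patients may consent less often, and offers inclusion of deceased patients as the remedy.

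**The concern.** When the clock starts at initiation but entry requires being alive at a later date, the time in between is survival that could not have ended in an observed death. Plain Kaplan-Meier counts it as time at risk. The patients who would have died in that window are absent altogether.

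This is not volunteer bias. It would arise even if every living patient consented. The remedy in 9.9 addresses it wherever deceased patients can be included, but is unavailable in exactly the places where it arises.

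Two results are exposed. OS and DFS are secondary endpoints, and Section 9.9 plans to set the study against trial and historical data, so an upward error would flatter Blincyto. The specified-AE proportions are primary. A patient who dies of such an event before consent leaves both numerator and denominator. Section 9.7.2.3.4 also plans results by country, so differences in consent law could appear as differences between countries.

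**Working it through.** **The protocol's own figures.** It gives no survival rate, no consent lag and no share of patients in consent-requiring countries. The nearest benchmark is the precision in Table 3. At N = 200 and a proportion of 50%, 1.96 × √(0.5 × 0.5 / 200) = 6.9 points, as printed. At 40% it is 1.96 × √(0.4 × 0.6 / 200) = 6.8 points, as printed.

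**Direction.** Let S be survival from initiation and D the time from initiation to consent. In an affected place only patients with survival time greater than D are enrolled. At any t beyond the longest lag, the naive estimate targets S(t) / E[S(D)]. The denominator is below 1 for any positive lag, so the estimate is too high. For DFS, every excluded patient has already had an event, since death counts.

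**Size, under stated assumptions.** Exponential survival with rate λ = ln 2 / median; medians of 6, 9 and 12 months; D uniform over 0–4 months (one review interval taken as the maximum lag); a share f of initiators in affected places, 25% or 50%. All four are assumptions; only the 4-month review interval is the protocol's.

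- E[S(D)] = (1 − exp(−4λ)) / (4λ)
- Naive 12-month OS in affected places = S(12) / E[S(D)]
- Pooled naive 12-month OS = S(12) / (f × E[S(D)] + 1 − f)

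| Median OS (months) | True 12-month OS | E[S(D)] | Naive, affected places | Pooled, f = 25% | Pooled, f = 50% |
|---|---|---|---|---|---|
| 6 | 25.0% | 0.801 | 31.2% | 26.3% (+1.3) | 27.8% (+2.8) |
| 9 | 39.7% | 0.861 | 46.1% | 41.1% (+1.4) | 42.7% (+3.0) |
| 12 | 50.0% | 0.893 | 56.0% | 51.4% (+1.4) | 52.8% (+2.8) |

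Worked line for median 6, f = 50%: 0.25 / (0.5 × 0.801 + 0.5) = 0.25 / 0.900 = 27.8%. The share of initiators in affected places who die before consent is 1 − E[S(D)]: 20%, 14% and 11%.

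**Does delayed entry correct OS?** A simulation of 20,000 patients with median OS of 8 months and lag uniform over 0–4 months has true 6-month OS of 59.5%. The naive estimate was 62.2% with 25% affected, 64.6% with 50% and 70.6% with all affected. Kaplan-Meier with risk starting at entry gave 59.8%, 59.5% and 59.1%. In this simulation entry is independent of prognosis.

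**Early fatal events.** If a share p of initiators would have a specified AE that is fatal before consent, the observed proportion is (1 − f)p / ((1 − f) + f(1 − p)). For p = 2%: 0.015 / 0.995 = 1.5% at f = 25%, 0.010 / 0.990 = 1.0% at f = 50%, and 0% if all are affected. Delayed entry cannot restore these events.

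**The case against.** **The condition may never be met.** The protocol names no country where consent is mandatory and deceased charts are barred, and it opens several routes around the problem: proxy consent, waiver, and consent for deceased patients' data. Countries are also chosen partly on local feasibility. This stands: the affected share could be zero, so a reader should not infer that the study's survival is shown to be overstated.

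**The lag is assumed.** The 4-month interval is between chart reviews; it does not date consent, and Appendix B lists consent under baseline. Patients who start after a site opens might consent close to initiation. This also stands.

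**A larger figure is tempting.** A lag of 0–12 months, as at a late-opening site's first review, gives 46%, 61% and 69% in affected places against true values of 25%, 40% and 50%, and 3–8 points pooled. Applying that lag to all initiators is not supported, because open sites are reviewed every 4 months. It bears only on patients enrolled at such a first review.

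**The population is mixed.** Section 7.1 calls the prognosis unfavourable for adults with R/R ALL, who are about 130 of the planned 200–300 patients in Section 9.5. MRD-positive and paediatric patients are included, and DFS is defined only for MRD-positive patients. The 6–12 month medians therefore have no source in the protocol.

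**Consequences can be over-read.** Section 7.1 says neurologic events are most frequent in the first week; it does not say that they are fatal. A reader might infer that all grade 4 or higher events are under-counted. That needs those events to be linked to death before consent, and the protocol gives no data on this.

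**The effect is within sampling error, and the SAP may deal with it.** An error of 1–3 points is below the 6.8–6.9 point half-width at N = 200 in Table 3, though it does not shrink with more patients. A SAP, not available here, could define risk-set entry. It could not make 9.9's remedy available where deceased patients are excluded, nor restore early fatal events. The country tables overlap with the proposed ones but do not separate sites by whether all initiators could be included.

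**Conclusion.** The point holds as a conditional one. Wherever consent is mandatory and neither deceased charts nor proxy consent can be used, the protocol as written credits survival from initiation to consent as time at risk. There OS and DFS are biased upward, and AEs fatal before consent are lost. Section 9.9 names volunteer bias but not this mechanism.

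The direction follows from the definitions; the size does not follow from the protocol. With a lag uniform over 0–4 months, exponential median OS of 6–12 months and 25–50% of initiators affected, pooled 12-month OS is about 1–3 points too high. The error is larger among patients enrolled at a late-opening site's first review and nil if no country is affected. No size is claimed for DFS, and no bias is claimed for non-fatal grade 4 or higher events. This is a cheap improvement to analysis and reporting; it does not invalidate the study.

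**What to change.** 1. In Section 9.7.2, add an OS and DFS analysis in which patients at sites where deceased patients could not be included enter the risk set at their consent or enrolment date (delayed-entry Kaplan-Meier). Initiation date is listed in Section 9.3.3. Appendix B lists consent and enrolment but does not specify a date field, so record that date in the eCRF if it is not already captured.
2. Next to the total population, present OS and the specified-AE tables (overall and fatal) for sites where all initiators, living and deceased, could be included.
3. In Section 9.9, name survival-to-consent bias separately from volunteer bias. State that delayed entry assumes entry is independent of prognosis, an assumption that 9.9's own worry about sicker patients puts in doubt, and that it does not recover early fatal events.

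Cost: analysis wording, one extra table set and possibly one eCRF date. Intervals will be wider early in the curve, survival figures may be slightly less favourable, and a patient who relapsed before consent will contribute nothing to the delayed-entry DFS analysis.
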